Depression*	CIHI/ODB/OHIP
Diabetes mellitus	ORRS/CIHI-DAD/OHIP
Fracture	CIHI-DAD/OHIP
Heart failure ++	CIHI-DAD
Hemorrhage	OHIP/CIHI-DAD
Hypertension	ORRS/ CIHI-DAD/OHIP
Hypotension	CIHI-DAD
Ischemic Stroke ++	CIHI-DAD
Liver Disease	ORRS/ CIHI-DAD/OHIP

Lung disease (COPD)	ORRS/ CIHI-DAD/OHIP
Malignancy	ORRS /CIHI-DAD/OHIP
Myocardial infarction ++	ORRS/ CIHI-DAD
Other serious illness that would shorten life expectancy less than 5 years	ORRS
Peripheral vascular disease	ORRS/ CIHI-DAD/OHIP
Smoking	ORRS
Stroke/Transient ischemic attack	ORRS/CIHI-DAD
Subarachnoid Hemorrhage	CIHI-DAD
Syncope	CIHI-DAD
Drugs (for 65+ years)	
ACE Inhibitors	ODB
ARB	ODB
Anti-depressants	ODB
Anti-Psychotics	ODB
Benzodiazepine	ODB
Beta-Blockers	ODB
Healthcare Utilization	
Long term care facility utilization	ODB/OHIP/CCRS
Number of nephrology consults in the last 12 months	OHIP
Number of Family Doctor consults in the last 12 months	OHIP
Number of Hospitalizations in last 12 months	CIHII-DAD
Number of Visits to Emergency Department in last 12 months	NACRS
Total Healthcare Costs in last 12 months	Various sources at ICES 
Lab Data (Last measured)	
Hemoglobin	ORRS/OLIS
Urea	ORRS/OLIS
eGFR	ORRS/OLIS
Serum Albumin	ORRS/OLIS
Procedures / Monitoring	
Carotid endarterectomy	OHIP
Coronary angiogram	OHIP/CIHI-DAD
Coronary revascularization	OHIP/CIHI-DAD
Echocardiography	OHIP/CIHI-DAD
Holter monitoring	OHIP/CIHI-DAD

Other Variables	
Dialysate Temperature (baseline)	Case Report Forms**
Pre-dialysis systolic blood Pressure (baseline)	Case Report Forms**
Pre-dialysis diastolic blood pressure (baseline)	Case Report Forms**
Mean intra-dialytic nadir systolic blood pressure (baseline)	Case Report Forms**
Diastolic blood pressure accompanying the intra-dialytic nadir systolic blood pressure (baseline)	Case Report Forms**
Date of first nephrology visit	ORRS
Height	ORRS
Last measure weight	ORRS
Body Mass Index (BMI)	ORRS
History of Renal Transplant	ORRS /CIHI-DAD/OHIP
First Dialysis Modality	
Peritoneal Dialysis	ORRS/CORR
Hemodialysis	ORRS/CORR
Had a late nephrology referral	ORRS/CORR
Vascular access used at index date (April 01, 2017)	
Arteriovenous fistula	ORRS/CORR
Arteriovenous graft	ORRS/CORR
Central venous catheter	ORRS/CORR
Hemodialysis Characteristics at Index Date	
Patients Dialyzing in an Acute Care Hospital	ORRS
Patients Dialyzing in a Chronic or Community Hospital	ORRS
Duration of all dialysis modalities (Months)	ORRS

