### Baseline Patient Characteristics

Baseline characteristics will be obtained through administrative data and center-level survey reporting. A list of baseline characteristics and database sources is available in appendix 7 of [name] et al. Continuous data will be summarized using means (standard deviations) or medians (25th, 75th percentiles) as appropriate. Binary and categorical variables will be summarized using counts and percentages. We expect to report a key set of baseline characteristics in the primary paper, with additional characteristics provided in an appendix.

We will use the Registered Persons Database supplied from the Ontario Ministry of Health and Long-term Care and enriched with other data sources at ICES to obtain demographic information. Kidney characteristics will be obtained from ORRS and the Canadian Organ Replacement Registry. Baseline outpatient medication dispensing will be obtained through the Ontario Drug Benefit (ODB) database using a 120-day lookback before the index date. Health care use in the year before the index date and baseline characteristics in

the 5 years before the index date will be assessed using the Ontario Health Insurance Plan Claims Database (OHIP), the Canadian Institute for Health Information Discharge Abstract Database (CIHI-DAD), CIHI's Same Day Surgery database, and the National Ambulatory Care Reporting System database. The OHIP Claims Database is supplemented with the ICES Physician Database and the Corporate Provider Database to obtain data on health care use with specific provider types. Long-term care status will be obtained from ODB, OHIP, and the Continuing Care Reporting System. Baseline laboratory information in the year before the index date will be obtained through the Ontario Laboratories Information System. We will use ICES-derived cohorts to determine the history of certain chronic conditions such as diabetes, congestive heart failure, hypertension, and chronic obstructive pulmonary disease. Whenever possible, we will use validated algorithms to define baseline variables that have been used in multiple prior studies.

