We will assess the intervention's effect on the rate of the primary outcome using the multivariable generalized-estimating-equations extension for the Fine and Gray's subdistribution proportional hazards, with an exchangeable covariance matrix, to account for the clustering of patients within hemodialysis centers and the competing risk of noncardiovascular death. We will supplement the primary analysis with the cause-specific hazard model for both the primary outcome and competing-risk of noncardiovascular death. We also will explore the composite of our primary event with the competing risk as described in the "Additional Analyses" section below.

As our study used covariate-constrained randomization, we will adjust for constrained covariates in our analyses; these patient-level covariates include age, biological sex, rural status, race, modified Charlson comorbidity index, number of unique hospital admissions (in the 12 months before the index date), number of unique hypertensive prescriptions, referral to a nephrologist  $< 3$  months before initiating dialysis, type of vascular access on the index date, serum albumin on the index date, and the following baseline comorbidities: myocardial infarction, congestive heart failure, peripheral vascular disease, and diabetes mellitus. We will also adjust for the cluster-level historical rate of the composite outcome of cardiovascular-related death and major cardiovascular-related hospitalization.

We will evaluate and report the model assumptions for the clustered subdistribution hazard and cause-specific hazards models. Appropriate techniques will be applied when model assumptions are violated. Specifically, this model assumes a linear relationship between the log hazard and covariates. We will assess the assumption for linearity using residual plots. From historic data, we expect that the linearity assumption will be violated for our continuous covariates. If this occurs, we plan to correct for the nonlinear covariates using restricted cubic splines. We will assess the proportionality of the hazard visually and use the Schoenfeld test for the intervention. If the assumption of proportionality is violated, we will consider alternative methods so that the model remains valid (ie, a time-stratified model to identify constant hazard ratios within appropriate time intervals).

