We will explore a range of prior distributions (see Appendix 1 and Table 1 in the Supplemental Material) that can condition the posterior distribution. We will use priors to reflect varying degrees of enthusiasm and skepticism for the benefit of a personalized temperature-reduced dialysate before starting MyTEMP. The parameter's estimate and standard errors will be obtained from the analysis (as described in the "Analysis of the primary outcome" section above) and combined with prior distributions to obtain the model's posterior distributions. We will estimate the Bayes factor and credible intervals using Markov chain Monte Carlo sampling techniques with at least 3 parallel chains. We will report the probability of the truth of our conclusions. This approach enables the specification of prior information, controls the sampling, and obtains posterior summary statistics and convergence diagnostics. The convergence of the generated Markov chain will be assessed by examining the trace plot, autocorrelation function plot, and posterior density plot.

**Analysis of the key secondary outcome.** The between-group difference in the key secondary outcome (the mean drop in patients' intradialytic systolic blood pressure) will be obtained using an unadjusted, generalized linear mixed model on the cluster-period summaries that accounts for the repeated measurements at the cluster level over time using longitudinal analysis methods, and appropriate CIs will be generated as described in section "Confidence Intervals and *P* Values: Level of Statistical Significance" in the "Statistical Principles" section above.

**Analysis of other secondary outcomes.** We will use the same analytic approach as for the primary outcome to examine each component of the primary outcome separately and the other secondary time-to-event outcomes (ie, see secondary outcomes listed in "Confidence Intervals and *P* Values: Level of Statistical Significance" and "Outcome Definitions" sections). Death (or noncardiovascular-related death) will be treated as a competing-risk event in these analyses when not part of the outcome. The model assumptions will be assessed as described in the "Analysis of the primary outcome" section, above.

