The number of all-cause hospital admissions and emergency department visits during the study period will be analyzed using a negative binomial model relevant for count data while adjusting for clustering of dialysis centers with generalized estimating equations and using the log of time as an offset. We have chosen a negative binomial model because the historic data show a propensity for overdispersion (ie, the mean and variance of all-cause hospitalization and emergency room visits appear to be different). We will assess model assumptions and evaluate the fit of our model. From historic data, we expect that 85% of our cohort will have at least 1 hospital admission and/or emergency department visit in follow-up, and we also expect this outcome to be right skewed. We will perform and report model diagnostics.

The four definitions of intradialytic hypotension will be analyzed at the center level in a similar manner as the key secondary outcome (ie, unadjusted, generalized linear mixed model on the cluster-period summaries).

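### The count models for emergency visits and admissions name no covariates, and the prior-year emergency-visit count is collected but placed in no adjustment set

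*Combined protocol and SAP*

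**What the plan says.** - **Count models.** The SAP, Analysis of other secondary outcomes, gives the form, the treatment of clustering and the exposure term ("negative binomial model relevant for count data while adjusting for clustering of dialysis centers with generalized estimating equations and using the log of time as", meaning the offset), and nothing else. The final protocol, Analysis of other outcomes, likewise mentions only within-centre clustering.
- **Adjustment rule.** The SAP, Analysis of the primary outcome, says "As our study used covariate-constrained randomization, we will adjust for constrained covariates in our analyses". The list that follows includes "number of unique hospital admissions (in the 12 months before the index date". It does not include prior emergency visits.
- **Reach of that rule.** The sentence sits under the primary outcome. The next section carries the primary approach over to the components and the other time-to-event outcomes, and does not mention counts.
- **Contrast.** For the key secondary outcome the SAP specifies an "unadjusted, generalized linear mixed model on the cluster-period summaries", and it says the same for intradialytic hypotension. The count models carry no such label.
- **Data held.** Appendix 7 of the final protocol lists both "Number of Hospitalizations in last 12 months" and "Number of Visits to Emergency Department in last 12 months". The SAP, Baseline Patient Characteristics, sets the window as "Health care use in the year before the index date".
- **Index date.** Under SAP Eligibility Criteria, a patient who starts in-centre treatment after 3 April 2017 is indexed on the day the 90-day stability rule is met.

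The 2022 corrigendum does not change any of this.

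**The concern.** A patient's own prior-year count is normally among the best predictors of the same count in follow-up. Aggregated over a centre, it also picks up local differences in how emergency departments are used. In a trial of 84 centres, such differences can dominate the standard error.

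The plan leaves two things unsettled. First, an analyst cannot tell whether the constrained covariates enter the count models. Second, even if they do, the emergency-visit outcome still lacks its own baseline value.

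These outcomes lie outside the six that are tested in order after the primary and key secondary. The final protocol, Statistical Significance, limits additional outcomes to estimates with unadjusted 95% intervals, so interval width is all the precision the reader gets. About 85% of patients are expected to have at least one admission or emergency visit.

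The look-back matters as well. For a later entrant, up to 90 of the 365 days before the index date (90/365 = 25%) fall after in-centre treatment began under the centre's allocated protocol. A covariate measured over that window can be affected by allocation.

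**Working it through.** **1. Which baseline counts enter, under each reading**

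| Reading of the adjustment sentence | Prior admissions | Prior emergency visits |
|---|---|---|
| Primary and time-to-event outcomes only | not in count models | not in count models |
| All analyses | in count models | not in count models |

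The emergency-visit gap is present in both rows. The admissions gap is present only in the first.

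**2. The plan's own power figure**

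The documents give no power or interval width for the count outcomes, so the cluster rate formula is first checked on the primary outcome:

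z = sqrt[(c−1)(λ0−λ1)² / {(λ0+λ1)/y + k²(λ0²+λ1²)}], power = Φ(z − z_{1−α/2})

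Inputs from Statistical Power and Appendix 11a: c = 42 per arm, y = 163 person-years, λ0 = 0.095, λ1 = 0.80 × 0.095 = 0.076, k = 0.216, α = 0.04.

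- Within-centre term: 0.171/163 = 0.001049
- Between-centre term: 0.216² × 0.014801 = 0.000691
- z = sqrt(41 × 0.019²/0.001740) = 2.917, so power is 80.6%. The plan states 80%.

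**3. The same formula for emergency visits**

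Appendix 10 gives 1.05 per person-year. It is labelled a hazard rate; using it as a count rate is an assumption. Also assumed: k = 0.216 carried over from the primary outcome, rate ratio 0.90 (λ1 = 0.945), α = 0.05.

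- Within-centre term: 1.995/163 = 0.01224
- Between-centre term: 0.046656 × 1.9955 = 0.09310, which is 0.09310/0.10534 = 88% of the variance
- z = sqrt(41 × 0.105²/0.10534) = 2.071, so power is 54.4% unadjusted

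Now let the prior count have correlation 0.5 with the outcome, so that the variance it acts on is multiplied by 1 − 0.25 = 0.75:

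- Acting on both terms: z = 2.071/sqrt(0.75) = 2.392; power 66.7%; interval 13% narrower.
- Acting on the within-centre term only: variance 0.00918 + 0.09310 = 0.10228; z = 2.102; power 55.7%; interval 1.5% narrower.

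Almost all of the possible gain therefore depends on whether prior counts predict differences between centres. In the favourable case, the gain at k = 0.15, 0.18, 0.20, 0.216, 0.25 and 0.30 is 9.8, 12.1, 12.4, 12.3, 11.2 and 9.0 points. The formula uses Poisson variation within centres, whereas the SAP expects overdispersion.

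**4. Simulation of the model itself**

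The set-up was 84 centres, about 13,500 patients, negative binomial GEE with robust standard errors and a log-time offset, and 60 replicates per scenario. Each was fitted with and without the outcome's own log(1 + prior count) and its square. Assumed ranges, none from the documents: patient frailty variance 0.5-1.5, prior-to-follow-up frailty correlation 0.3-0.6, between-centre CV 0.1-0.2, centre-level correlation 0.5-0.9.

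Ratio of mean robust standard errors, adjusted to unadjusted:

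- Emergency visits (1.05): 0.78 to 0.97
- Admissions (0.65): 0.83 to 0.98
- Prior counts carrying no information on centre differences (emergency visits): 1.00
- Allocation constrained to a 10% standardized difference on the prior count: 0.83 (emergency visits), 0.87 (admissions)

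The comparator throughout is a model with no covariates. The gain from adding emergency visits to the constrained set was not simulated.

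**The case against.** The strongest reply is that the SAP already handles most of this. Its adjustment sentence refers to analyses in the plural, the final protocol says its analyses will account for the constrained randomization, and the SAP writes unadjusted where it means it. On that reading the count models already contain prior admissions, age, comorbidity, vascular access, albumin and more. Only prior emergency visits are absent, and leaving them out is a defensible prespecified choice. This largely stands. It reduces the admissions part to a request for clarification but does not close the emergency-visit gap.

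A reader might infer more than the documents support:

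- **That power rises from 54% to 67%.** This compares with a wholly unadjusted model and needs the 0.5 correlation to act on the between-centre term. The documents give neither a correlation nor a between-centre CV for these outcomes. Power is also a secondary measure for outcomes that are not tested.
- **That the plan cannot exclude the hospitalization ratios of 1.10 and 1.12 cited in Appendix 1, section 1.3.** Those are observational estimates whose intervals include 1 (95% CI 0.94-1.29 and 99% CI 0.98-1.27). They concern hospitalization, whose baseline may already be adjusted for.
- **That three count models are affected.** The analysis section names two. The composite of emergency visits or hospitalizations is listed as an outcome, but the SAP does not say it is modelled as a count.

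**Conclusion.** The point holds as a minor improvement with one ambiguity to settle. The count-model text names no covariates, and prior-12-month emergency visits are collected but used in no adjustment set on either reading. Prior admissions may already be included.

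The expected benefit is a narrower 95% interval, mainly for emergency visits. Against an unadjusted model, the simulation puts it at about 2-22% under the assumed inputs. It would be smaller if the constrained covariates already apply, and near zero if prior counts carry no information on centre differences. The direction is likely but not guaranteed, and the documents do not allow the size to be derived. The primary result and the tested hierarchy are unaffected.

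**What to change.** In the SAP, Analysis of other secondary outcomes, state that:

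1. The emergency-visit and admission count models adjust for the constrained covariates listed under Analysis of the primary outcome, with prior admissions entered once, through that list.
2. Both models also include log(1 + prior-12-month emergency visits) as a patient-level covariate.
3. For patients entering after 3 April 2017, the 12-month window for prior emergency visits, and for prior admissions in these models, ends at the first in-centre treatment rather than at the index date.

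The cost is a few sentences, a slightly larger model and one extra look-back definition beside the index-date window used elsewhere. No new data source is needed, but the two counts must be re-derived for later entrants.

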### Additional Analyses

We will conduct several additional analyses to assess the robustness of the results of the primary analysis. We will conduct an as-treated analysis (see the "Analysis Populations" section, above). We will also conduct a additional competing-risk analysis, a recurrent-event analysis, and prespecified subgroup analyses.

**Competing-risk events.** Additional events that may influence a patient's chance of experiencing the primary outcome include receipt of a kidney transplant, switching to a non-in-center hemodialysis modality, and emigrating from the province. As such, we will conduct additional analyses and treat these events as competing risks. We will report how often these events occur during the follow-up period (see Figure 2 in the Supplemental Material for more detail) and examine the extent to which treating these as competing events impacts our estimate of the intervention effect.

**Recurrent events.** In an analysis of historical data, over a 4-year follow-up period predating the trial, we found that 19% of patients experienced at least one event in our primary composite outcome. Only 4% of all patients experienced more than one event. Given the infrequent number of recurrent events, we decided to use a parsimonious approach of time-to-first event model for the primary analysis. However, we will repeat the primary analysis using a recurrent-event model such that patients may contribute multiple outcome events during the trial period. We will use a cluster analog of the mean and rate functions in a recurrent-event multivariate regression model to accommodate multiple events per patient while accommodating the clustered design using a marginal approach (ie, a common baseline rate function). We will define a hospitalization episode of care as a direct admission to an acute care hospital from which the patient has subsequently been discharged home (ie, a hospital discharge and admission within the same day is considered to all be part of the same episode of care, as this could be simply a transfer between hospitals).

**Subgroup analyses.** In our protocol, we have prespecified two subgroup analyses for the MyTEMP trial. We will simply provide point estimates and corresponding 95% CIs for subgroups and will not perform significance testing. First, a subgroup analysis of patients with preexisting cardiovascular disease (ie, patients hospitalized with myocardial infarction, ischemic stroke, or congestive heart failure at least once before study entry). Second, a subgroup of new hemodialysis patients, that is, those starting in-center hemodialysis for the first time during the trial period. These analyses will follow the same approaches as described above. We hypothesize that the intervention may confer a larger absolute benefit to these 2 subgroups of patients. To examine the presence of additive interaction, we will calculate the hazard ratios (and 95% CI) between the intervention and control groups in patients with and without preexisting cardiovascular disease, and in new hemodialysis patients versus those who were already receiving dialysis when the trial started on April 3, 2017.

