In the literature, the credibility of subgroup effects is generally low, even when claims about the treatment effect made by the researchers are strong. We will visually examine the point estimate of the hazard ratio for the primary outcome with its accompanying 95% confidence intervals across subgroups for consistency of the effect. Two prespecified subgroups of interest, where a personalized dialysis temperature may have a larger treatment effect, are (1) patients with a baseline prior hospitalization with myocardial infarction, ischemic stroke, or congestive heart failure, and (2) incident patients, defined as new patients starting in-center hemodialysis during follow-up

(based on historical data, approximately 9000 patients will start hemodialysis at a study center during the 4-year trial period).

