### Analytic Methods

For both the intervention and control groups, we will summarize the weighted proportion of the patients' observation time spent receiving hemodialysis at an index center (or a center providing the same allocated temperature protocol as the index center), the time spent receiving hemodialysis at other centers, and the time spent receiving other forms of kidney replacement therapy (as described in the "Adherence and Protocol Deviations" section, above, and in Figure 2 in the Supplemental Material). Patient crossovers between the intervention and control arms will also be reported.

**Analysis of the primary outcome.** The primary analysis will follow an intention-to-treat approach. Eligible patients will be analyzed according to their index center's treatment allocation (regardless of whether they transitioned to other dialysis centers or received other types of kidney replacement therapy in follow-up). Patients will be followed up until they experience the primary outcome, emigrate from Ontario, or die of a noncardiovascular cause (which will be treated as a competing-risk event).

We will report the crude frequency (%) and crude event rate (number of events per 100 person-years) for the time to first event for the primary composite outcome. We will create a graph of the nonparametric cumulative incidence function (CIF) showing the time followed, number of events, and patients at risk during regular intervals in the trial for the intervention and control groups. Noncardiovascular death will be treated as a competing-risk event. We will present the curves for visualization purposes only (no statistical tests will be conducted for differences between curves); we will simultaneously present the curves of the primary outcome, the components of the composite outcome, and the competing risk of noncardiovascular death.

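### The SAP hypothesizes a larger absolute benefit in two subgroups but examines additive interaction with hazard ratios, which measure interaction on the ratio scale

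*Combined protocol and SAP*

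**What the plan says.** The SAP's paragraph on subgroup analyses names two subgroups: patients hospitalized with myocardial infarction, ischemic stroke or heart failure before entry, and patients starting in-center hemodialysis during the trial. It states a hypothesis on the absolute scale: "We hypothesize that the intervention may confer a larger absolute benefit to these 2 subgroups of patients". It then names the measure: "To examine the presence of additive interaction, we will calculate the hazard ratios (and 95% CI) between the intervention and control groups", computed in patients with and without prior cardiovascular disease, and in new patients against those already on dialysis at trial start. The reporting is descriptive: "We will simply provide point estimates and corresponding 95% CIs for subgroups and will not perform significance testing". For methods there is a general pointer: "These analyses will follow the same approaches as described above".

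The methods it points to, under Analysis of the primary outcome, contain these elements:

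- Descriptive rates: "We will report the crude frequency (%) and crude event rate (number of events per 100 person-years) for the time to first event".
- Nonparametric cumulative incidence curves by arm, for display only.
- A regression built on the "extension for the Fine and Gray's subdistribution proportional hazards" model, of which the SAP says "we will adjust for constrained covariates in our analyses".
- A risk difference between the arms' cumulative incidence functions, with a 95% CI, given only if the primary result is significant.

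The final protocol (Additional exploratory analyses) was less specific: "We will visually examine the point estimate of the hazard ratio for the primary outcome with its accompanying 95% confidence intervals across subgroups". It claimed no additive scale. The 2022 corrigendum to the SAP makes three changes, none of them to the subgroup paragraph.

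**The concern.** The purpose and the measure are on different scales. Additive interaction asks whether the risk (or rate) difference between arms is larger in one stratum than in the other. A comparison of stratum hazard ratios asks whether the proportional reduction differs. When the strata have different baseline risks, the two questions can have different answers:

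- Equal hazard ratios go with unequal absolute benefits.
- Equal absolute benefits go with unequal hazard ratios.
- A somewhat weaker hazard ratio in the higher-risk stratum can still go with the larger absolute benefit there.

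A reader who follows the paragraph as written could therefore take two similar hazard ratios as evidence against the hypothesis when the data support it. Because the SAP relies on estimates and intervals here rather than tests, the scale of those estimates is what readers will interpret.

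**Working it through.** **Does any other section supply the additive measure?** Crude rates and cumulative incidence curves may carry over through the general pointer, but the curves are for display only. The one absolute contrast with a CI is between trial arms and depends on a significant primary result, so it would not be required after a null one. A difference of risk differences between strata is planned nowhere.

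**Inputs.**
- Overall event rate 0.095 per person-year, coefficient of variation 0.216, 163 person-years per center, hazard ratio 0.80, two-sided alpha 0.04 (final protocol, Statistical Power); 42 centers per arm (Appendix 11a).
- Expected 21% with the primary outcome and 23% dying of noncardiovascular causes (SAP supplement, Figure 2 legend). As an approximation, the noncardiovascular death rate is m = 0.095 × 23/21 = 0.104 per person-year.
- About 13,500 patients (SAP, Randomization and Sample Size).
- *Assumed, because the documents give no subgroup rates:* two equal strata, rate ratio R between them of 1, 1.5, 2 or 3, constant hazards, the same m in all strata and arms.

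**The plan's own figure.** No subgroup figure is given. The stated 80% power does reproduce with the standard formula for cluster-randomized rates. With λ0 = 0.095 and λ1 = 0.076, the variance term is 0.171/163 + 0.216² × (0.095² + 0.076²) = 0.00174. Then 0.019 × √(41/0.00174) − 2.054 = 0.86, which is 80.6% power (81.6% with 42 in place of 41). The power figure is not in dispute.

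**Stratum rates.** Low = 0.095/(0.5 + 0.5R); high = R × low.

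**Two-year cumulative incidence in controls.** CIF(h) = h/(h + m) × (1 − exp(−2(h + m))).

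**Benefit with 0.80 on the cause-specific hazard:** CIF(h) − CIF(0.8h). **Benefit with 0.80 on the subdistribution hazard,** the scale of the SAP's primary model: CIF − [1 − (1 − CIF)^0.8].

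| R | Rates high / low | Control CIF, % | Benefit, cause-specific (points) | Contrast | Benefit, subdistribution (points) | Contrast |
|---|---|---|---|---|---|---|
| 1 | 0.0950 / 0.0950 | 15.67 / 15.67 | 2.91 / 2.91 | 0 | 2.92 / 2.92 | 0 |
| 1.5 | 0.1140 / 0.0760 | 18.48 / 12.76 | 3.38 / 2.41 | 0.97 | 3.40 / 2.42 | 0.98 |
| 2 | 0.1267 / 0.0633 | 20.29 / 10.76 | 3.67 / 2.05 | 1.62 | 3.70 / 2.06 | 1.64 |
| 3 | 0.1425 / 0.0475 | 22.50 / 8.20 | 4.02 / 1.58 | 2.44 | 4.05 / 1.58 | 2.47 |

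In every row the two stratum hazard ratios are both 0.80.

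**Reversed order.** At R = 2, with a cause-specific hazard ratio of 0.88 in the higher-risk stratum and 0.80 in the lower, the benefits are 2.18 and 2.05 points. The stratum with the weaker hazard ratio still gains more.

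**The converse.** With assumed rates of 16 and 6 per 100 person-years and an equal reduction of 1.6, there is no additive interaction on the rate scale, but the rate ratios are 1 − 1.6/16 = 0.90 and 1 − 1.6/6 = 0.73.

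**Sensitivity at R = 2, cause-specific version.**
- m from 0.05 to 0.15: 3.9 v 2.2 to 3.5 v 2.0 points.
- Higher-risk share from 30% to 70%: 4.1 v 2.3 to 3.3 v 1.8 points.
- Overall rate 0.08 to 0.11 (the range in Appendix 11a), m held at 0.104: 3.2 v 1.8 to 4.1 v 2.3 points.

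The benefit ratio is about 1.8 throughout.

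**Precision.** With 13,500/4 = 3,375 patients per arm and stratum, summing p(1 − p)/n over the four cells gives a standard error of 1.17 to 1.20 points. The 95% half-width is 1.96 times that, about 2.3 points (2.1 to 2.9 for shares of 30% to 70%). This ignores clustering and treats all patients as followed for 2 years, so it is optimistic.

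**The case against.** The strongest reply is that this is a wording slip in an exploratory analysis. Subgroups are untested, the protocol itself rates subgroup credibility as generally low, and results will be labelled as unadjusted for multiplicity. If crude rates by arm carry into the subgroups, a reader could work out rate differences. Hazard ratios against a common reference group can also yield an additive measure, the relative excess risk due to interaction. The illustration rests on invented stratum rate ratios and on rates that predate the corrigendum, whose third change redefines cardiovascular death and so shifts the split between primary events and noncardiovascular deaths. The added estimate would be imprecise.

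Much of this stands, and it limits how much the point matters. It does not remove it. The contrasts named are intervention against control within each stratum, not against a common reference, so no relative excess risk is planned. Rates from which a reader might compute a difference are not a prespecified contrast with an interval. The general pointer does not override a sentence that ties additive interaction to hazard ratios by name. The outdated rates affect only an illustrative size; moving the overall rate between 0.08 and 0.11 leaves the benefit ratio at about 1.8. Imprecision is a reason to show the interval, not to substitute a measure on another scale.

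**Conclusion.** The concern holds. As written, the subgroup paragraph can give the wrong answer to its own hypothesis, and nothing else in the SAP, protocol or corrigendum supplies the missing additive contrast. Under the stated assumptions, identical hazard ratios of 0.80 hide an additive contrast of about 1.0, 1.6 and 2.4 to 2.5 points at 2 years for rate ratios of 1.5, 2 and 3. Those sizes are illustrative. Higher risk in patients with prior cardiovascular disease is an assumption. For new patients the direction is not established: the protocol's figure of 20% to 40% dying within a year of starting dialysis is for all causes and does not apply the 90-day rule. The mismatch of scale does not depend on these numbers. It should be corrected, but it does not touch the primary estimate, alpha or power.

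**What to change.** In the SAP's subgroup paragraph:

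1. For each subgroup level, report the between-arm difference in cumulative incidence of the primary outcome at a fixed time that all strata can reach, for example 2 years. Entry runs to March 1, 2021 and follow-up ends on March 31, 2021, so the time must suit the later-entering new patients.
2. Report the difference between the two stratum differences as the estimate of additive interaction.
3. Take 95% CIs from a bootstrap that resamples centers within arm, and report these results whatever the primary p-value.
4. State whether the differences are unadjusted or standardized to the covariates of the primary model. If unadjusted, label them so, because they will stand beside adjusted hazard ratios. If standardized, repeat the covariate model and any imputation of serum albumin within each bootstrap sample.
5. Keep the hazard ratios, labelled as ratio-scale (multiplicative) interaction.

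If no absolute measure is added, the minimum is to replace the word additive and remove the word absolute, so that the hypothesis matches the analysis.

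The minimum is an edit to one paragraph. The unadjusted version is a modest addition to the planned cumulative incidence functions; the standardized version is more work. Neither needs new data. The price is wide intervals: at least plus or minus 2.3 points with equal strata, against an illustrative contrast of 1.0 to 2.5.
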